8.0 Adverse Events and Reporting Requirements

8.1 Monitoring, Recording and Reporting of Adverse Events

An AE is any noxious, unintended, or untoward medical occurrence that may appear or worsen in a subject during the course of a study. It may be a new intercurrent illness, a worsening concomitant illness, an injury, or any concomitant impairment of the subject's health, including laboratory test values (as specified by the criteria below), regardless of etiology. Any worsening (ie, any clinically significant adverse change in the frequency or intensity of a pre-existing condition) should be considered an AE. A diagnosis or syndrome should be recorded on the AE page of the eCRF rather than the individual signs or symptoms of the diagnosis or syndrome.

An overdose, accidental or intentional, whether or not it is associated with an AE, or abuse, withdrawal, sensitivity or toxicity to an investigational product (IP) should be reported as an AE. If an overdose is associated with an AE, the overdose and AE should be reported as separate terms.

All subjects will be monitored for AEs during the study. Assessments may include monitoring of any or all of the following parameters: the subject's clinical symptoms, laboratory, pathological, radiological or surgical findings, physical examination findings, or other appropriate tests and procedures.

Related AEs will be recorded by the Investigator from the time the subject signs informed consent to 30 days after the last dose of IP. The Investigator or physician designee is responsible for providing source documentation and assigning attribution for all AEs. Only related adverse events and SAEs will be recorded on the AE page of the eCRF and in the subject's source documents.

Adverse events and protocol specific data will be entered into PDMS/CORe. PDMS/CORe will be used as the electronic case report form for this protocol.

All SAEs must be reported to Astex Drug Safety within 24 hours of the investigator's knowledge of the event by facsimile, or other appropriate method, using the SAE Report Form, or approved equivalent form.

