1.3.2 Secondary Endpoints

The secondary endpoints are:

- 1.3.2.1 Safety (type, frequency, severity of AEs and relationship of AEs to SGI-110)
- 1.3.2.2 Overall response rate
- 1.3.2.3 Duration of remission
- 1.3.2.4 Incidence of acute and chronic graft versus host disease (GVHD)
- 1.3.2.5 Overall survival and disease free survival at one year after study enrollment

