4.4.1 Hematologic Toxicity

4.4.1.1 Cohort 1:

- 4.4.1.1.1 No dose reductions, delays or modifications are required for hematologic toxicities during the treatment cycles given with an intent to achieve CR/CRi. It is assumed that low counts observed in the presence of active disease (no morphological remission) are due to involvement by the disease and require treatment for improvement. Patients will not require dose modifications for hematological toxicity before they are reported to achieve morphological remission.
- 4.4.1.1.2 For patients who achieve complete morphological remission (CR/CRi) on study, they will receive the subsequent cycles (given as maintenance therapy) approximately every 28 days, provided that their peripheral blood counts have recovered (ANC>=1.0 X 10⁹ /L and platelet count>=50 X 10⁹/L)). If the peripheral count recovery is delayed beyond 42 days from Day 1 of the prior cycle and the delay is presumed to be secondary to therapy (after confirmation of achieving morphological remission), the SGI-110 doses may be reduced at least by one level for subsequent doses (e.g. from 40 to 30 mg).

4.4.1.2 Cohort 2:

- 4.4.1.2.1 No dose reductions, delays or modifications are required for hematologic toxicities during the treatment cycles given in the continuous presence of MRD. It is assumed that low counts in the presence of MRD are due to disease involvement and require treatment for improvement. Indeed, the dose level of SGI-110 can be increased at least one dose level at the discretion of treating physician and principal investigator if persistency of MRD is documented at any time point of disease assessment while on study independent of hematological toxicities observed as indicated at 4.2.2.4.
- 4.4.1.2.2 After the documentation of MRD negative status with the SGI-110 treatment, if the peripheral count recovery is delayed beyond 42 days from Day 1 of the prior cycle and the delay is presumed to be secondary to therapy, the SGI-110 doses may be reduced at least by one level for subsequent doses (e.g., from 30 to 20 mg).
- 4.4.1.3 Cohort 3: If the peripheral count recovery is delayed beyond 42 days from Day 1 of the prior cycle and the delay is presumed to be secondary to therapy, the SGI-110 doses may be reduced at least by one level for subsequent doses (e.g., from 30 to 20 mg).

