If an AE is considered serious, both the AE page/screen of the eCRF and the SAE Report Form must be completed.

For each SAE, the Investigator will provide information on severity, start and stop dates, relationship to IP, action taken regarding IP, and outcome.

Recommended Adverse Event Recording Guidelines					
Attribution	Grade 1	Grade 2	Grade 3	Grade 4	Grade 5
			Phase I	Phase I	Phase I
Unrelated	Phase I	Phase I	Phase II	Phase II	Phase II
			i ilase ii	Phase III	Phase III
Unlikely	Phase I	Phase I	Phase I	Phase I	Phase I
				Phase II	Phase II
			Filase II	Phase III	Phase III
	Phase I	Phase I	Phase I	Phase I	Phase I
Possible	Phase II	Phase II	Phase II	Phase II	Phase II
	Filase II	Phase III	Phase III	Phase III	Phase III
	Phase I	Phase I	Phase I	Phase I	Phase I
Probable	Phase II	Phase II	Phase II	Phase II	Phase II
	Phase II	Phase III	Phase III	Phase III	Phase III
	Phase I	Phase I	Phase I	Phase I	Phase I
Definitive	Phase II	Phase II	Phase II	Phase II	Phase II
	FIIdSE II	Phase III	Phase III	Phase III	Phase III

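### Section 8.1 leaves non-serious grade 3-4 AEs judged unrelated or unlikely off the record, although the protocol's Phase II recording table asks for them and the safety endpoint is not limited to related AEs

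*Combined protocol and SAP*

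**What the plan says.** Section 8.1 sets the recording rule: "Only related adverse events and SAEs will be recorded on the AE page of the eCRF". The same sentence extends the limit to source documents. The window is given in the same section: "Related AEs will be recorded by the Investigator from the time the subject signs informed consent to 30 days after the last dose of IP". Yet 8.1 also makes the investigator or designee responsible for source documentation and for "assigning attribution for all AEs". Section 8.2 likewise has a qualified investigator evaluate every AE.

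Section 8.2.1 contains a grid headed "Recommended Adverse Event Recording Guidelines", with five attribution levels down the side and grades 1 to 5 across. For unrelated and unlikely events it lists Phase I alone at grades 1-2 and includes Phase II at grades 3, 4 and 5. For possible, probable and definitive events it includes Phase II at every grade. Section 4.1 describes this trial as single-arm phase II.

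Section 8.3 requires all SAEs to be reported and entered on the AE page regardless of relationship. Section 8.2.3 uses two causality levels, suspected and not suspected.

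The secondary endpoint in 1.3.2.1 reads "Safety (type, frequency, severity of AEs and relationship of AEs to SGI-110". It is not restricted to related events.

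**The concern.** The endpoint asks how often AEs occur, how severe they are and how they relate to SGI-110. Under 8.1 the answer to the last question decides whether a non-serious event is recorded at all. A relationship breakdown needs both the related and the unrelated events, and for non-serious AEs only the related ones are kept.

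There is no control arm to show whether attribution was sound. Patients have had a transplant and may have GVHD, immunosuppression and DLI. Under 8.2.3 an event that another medication, intervention or condition sufficiently explains is not suspected. A non-serious toxicity put down to DLI would therefore go unrecorded, although objective 1.2.1 concerns the safety of SGI-110 with or without DLI.

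Sites also face instructions that cannot all be met: assign attribution to every AE, but document only the related and serious ones. Different sites or staff may resolve this differently, and the AE tables would then mix two recording practices.

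**Working it through.** The plan states no figure on this point, so the check is mainly a comparison of text.

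**Step 1. Set the rules side by side for a Phase II trial.**

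| Event | Sections 8.1 and 8.3 | Table in 8.2.1 | Result |
|---|---|---|---|
| Any SAE, any attribution | Recorded | Grade 3-5 recorded | No loss |
| Grade 5 | Always serious, so recorded | Recorded | Agree |
| Non-serious, possible or stronger, any grade | Recorded | Recorded | Agree |
| Non-serious, unrelated or unlikely, grade 1-2 | Not recorded | Phase I only | Agree |
| Non-serious, unrelated or unlikely, grade 3-4 | Not recorded | Recorded | Conflict |

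The direct conflict is the last row. (The grade 3 cell of the unlikely row is hard to read in the text copy; I take it to list Phase II like its neighbours.)

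**Step 2. Compare the recorded data with the endpoint.** Let R be the number of non-serious related AEs. Non-serious unrelated AEs on record are 0 by rule. The related share among recorded non-serious AEs is R / (R + 0) = 100%, whatever the true share is.

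**Step 3. Show how the bias depends on unknowns.** Let q be the share of grade 3-4 AEs that are unrelated or unlikely, and s the share of those that are serious. The documents give neither, so both are assumptions.

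- Recorded fraction = (1 - q) + q × s
- Apparent related share = (1 - q) / recorded fraction

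For q = 0.50 and s = 0.20: 0.50 + 0.50 × 0.20 = 0.60, and 0.50 / 0.60 = 83%.

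| q | True related share | s | Recorded fraction | Apparent related share |
|---|---|---|---|---|
| 0.25 | 75% | 0 | 75% | 100% |
| 0.25 | 75% | 0.20 | 80% | 94% |
| 0.25 | 75% | 0.50 | 88% | 86% |
| 0.50 | 50% | 0 | 50% | 100% |
| 0.50 | 50% | 0.20 | 60% | 83% |
| 0.50 | 50% | 0.50 | 75% | 67% |
| 0.75 | 25% | 0 | 25% | 100% |
| 0.75 | 25% | 0.20 | 40% | 63% |
| 0.75 | 25% | 0.50 | 63% | 40% |

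The direction is the same in every row: frequency too low, related share too high. The size depends on q and s.

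**Step 4. See what the phase I figures in section 2.4 can show.** Related rate divided by all-cause rate:

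- fatigue: 8/15 = 53%
- nausea: 6/15 = 40%
- injection site pain: 15/15 = 100%

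Attribution can matter a good deal for some events and not at all for others. These rates carry no grade and do not separate serious from non-serious events, so they do not measure the gap found in Step 1.

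**The case against.** The strongest defence is that 8.1 is the trial-specific rule, while the table is a generic grid for Phases I to III headed as a recommendation. Seriousness is also defined broadly: any inpatient admission counts, whatever its length, and many grade 3-4 events will qualify. This stands in part. It narrows the gap, and a sponsor could choose to let 8.1 prevail. But nothing says that the table is overridden, and the mismatch with endpoint 1.3.2.1 and with the duty to attribute all AEs does not depend on the table.

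A reader might infer several stronger points that the documents do not support:

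- **That only related AEs are recorded, so the safety endpoint cannot be estimated.** Sections 8.1 and 8.3 capture every SAE regardless of cause. SAE rates, and rates of AEs attributed to drug, remain estimable.
- **That half or more of events would be lost.** The phase I rates are ungraded, injection site pain shows no loss, and SAE capture is left out. Unrelated grade 1-2 fatigue or nausea would go unrecorded under the table too. Diarrhea and febrile neutropenia are absent from the list of most common related events, but that does not give their related rates. Section 2.4 itself reports febrile neutropenia among related grade 3/4 events and as dose-limiting toxicity.
- **That section 4.4.1 builds misattribution into the data.** The sentence "It is assumed that low counts observed in the presence of active disease (no morphological remission) are due to involvement by the disease" explains a dose-modification rule, as does the statement on infections in 4.4.2.3. Neither is an instruction on AE attribution, although investigators could carry them over.
- **That GVHD is lost.** It is a separate endpoint (1.3.2.4), is tabulated under section 7 and is followed after discontinuation (8.4).
- **That nothing could be recovered.** Scheduled laboratory results (5.1) and local physicians' notes (5.4.5) would allow some reconstruction. Because 8.1 also restricts source documents, this is not assured.

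**Conclusion.** The point holds in a limited form. Section 8.1 conflicts with the Phase II entries of the protocol's own table for non-serious grade 3-4 AEs judged unrelated or unlikely, with its own requirement to attribute all AEs, and with a safety endpoint not confined to related events. If 8.1 is followed as written, all-cause grade 3-4 AE frequency is biased low and the relationship breakdown of non-serious AEs is fixed at 100% related.

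The direction of bias follows from the rule alone, provided some such events occur. The size cannot be derived from the documents; the grid above rests on assumed q and s. No sample size, stopping rule or efficacy analysis is affected. This should be corrected, but it does not undermine the trial's primary conclusions.

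**What to change.** Amend 8.1 to match the Phase II column of the table: record all grade 3-5 AEs whatever the attribution, related AEs of every grade, and all SAEs, in both the eCRF and source documents, with attribution as a data field.

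Map the two-level scale in 8.2.3 to the five levels in the table. The mapping matters because an event that is plausible in timing but sufficiently explained by something else is not suspected under 8.2.3, yet an investigator could reasonably call it possible in the table.

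Tabulate all-cause and related grade 3-5 rates side by side. Unrelated non-serious grade 1-2 events would still go unrecorded, so all-cause frequency should be described as grade 3-5 only.

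If recording is not widened, restate endpoint 1.3.2.1 as related AEs and SAEs only, and say that the table does not apply.

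The cost is additional data entry for non-serious grade 3-4 events. No new tests, visits or patients are needed, and no design figure changes.

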8.2 Evaluation of Adverse Events and Reporting to Astex Pharmaceuticals

A qualified Investigator will evaluate all AEs as to:

8.2.1 Seriousness

An SAE is any AE occurring at any dose that:

- Results in death
- Is life-threatening (ie, in the opinion of the investigator, the subject is at immediate risk of death from the AE)
- Requires inpatient hospitalization or prolongation of existing hospitalization (hospitalization is defined as an inpatient admission, regardless of length of stay)
- Results in persistent or significant disability/incapacity (a substantial disruption of the subject's ability to conduct normal life functions)
- · Is a congenital anomaly/birth defect
- Constitutes an important medical event

Important medical events are defined as those occurrences that may not be immediately life threatening or result in death, hospitalization, or disability, but may jeopardize the subject or require medical or surgical intervention to prevent one of the other outcomes listed above. Medical and scientific judgment should be exercised in deciding whether such an AE should be considered serious

Events **not considered** to be SAEs are hospitalizations for:

- A standard procedure for protocol therapy administration. However, hospitalization or prolonged hospitalization for a complication of therapy administration will be reported as an SAE.
- Routine treatment or monitoring of the studied indication not associated with any deterioration in condition.
- The administration of blood or platelet transfusion as routine treatment of studied indication. However, hospitalization or prolonged hospitalization for a complication of such transfusion remains a reportable SAE.
- A procedure for protocol/disease-related investigations (e.g., surgery, scans, endoscopy, sampling for laboratory tests, bone marrow sampling). However, hospitalization or prolonged hospitalization for a complication of such procedures remains a reportable SAE.

- · Hospitalization or prolongation of hospitalization for technical, practical, or social reasons, in absence of an AE.
- A procedure that is planned (ie, planned prior to starting of treatment on study) must be documented in the source document and the eCRF. Hospitalization or prolonged hospitalization for a complication remains a reportable SAE.
- An elective treatment of a pre-existing condition unrelated to the studied indication.
- Emergency outpatient treatment or observation that does not result in admission, unless fulfilling other seriousness criteria above.

If an AE is considered serious, both the AE page/screen of the eCRF and the SAE Report Form must be completed.

For each SAE, the Investigator will provide information on severity, start and stop dates, relationship to IP, action taken regarding IP, and outcome.

Recommended Adverse Event Recording Guidelines					
Attribution	Grade 1	Grade 2	Grade 3	Grade 4	Grade 5
			Phase I	Phase I	Phase I
Unrelated	Phase I	Phase I	Phase II	Phase II	Phase II
			i ilase ii	Phase III	Phase III
Unlikely	Phase I	Phase I	Phase I	Phase I	Phase I
				Phase II	Phase II
			Filase II	Phase III	Phase III
	Phase I	Phase I	Phase I	Phase I	Phase I
Possible	Phase II	Phase II	Phase II	Phase II	Phase II
	Filase II	Phase III	Phase III	Phase III	Phase III
	Phase I	Phase I	Phase I	Phase I	Phase I
Probable	Phase II	Phase II	Phase II	Phase II	Phase II
	Phase II	Phase III	Phase III	Phase III	Phase III
	Phase I	Phase I	Phase I	Phase I	Phase I
Definitive	Phase II	Phase II	Phase II	Phase II	Phase II
	FIIdSE II	Phase III	Phase III	Phase III	Phase III

8.2.2 Severity / Intensity

The severity / intensity of AEs will be graded based upon the subject's symptoms according to the currently active minor version of Common Terminology Criteria for Adverse Events (CTCAE, Version 4.0).

AEs that are not defined in the CTCAE should be evaluated for severity according to the following scale:

- Grade 1 = Mild transient or mild discomfort; no limitation in activity; no medical intervention/therapy required
- Grade 2 = Moderate mild to moderate limitation in activity, some assistance may be needed; no or minimal medical intervention/therapy required

- Grade 3 = Severe marked limitation in activity, some assistance usually required; medical intervention/therapy required, hospitalization is possible
- Grade 4 = Life threatening extreme limitation in activity, significant assistance required; significant medical intervention/therapy required, hospitalization or hospice care probable
- Grade 5 = Death the event results in death

The term "severe" is often used to describe the intensity of a specific event (as in mild, moderate or severe myocardial infarction); the event itself, however, may be of relatively minor medical significance (such as severe headache). This criterion is *not* the same as "serious" which is

based on subject/event *outcome* or *action* criteria associated with events that pose a threat to a subject's life or functioning.

Seriousness, not severity, serves as a guide for defining regulatory obligations.

8.2.3 Causality

The investigator must determine the relationship between the administration of IP and the occurrence of an AE/SAE as Not Suspected or Suspected as defined below:

Not suspected: The temporal relationship of the AE to IP administration makes

a causal relationship unlikely or remote, or other

medications, therapeutic interventions, or underlying conditions provide

a sufficient explanation for the observed event.

Suspected: The temporal relationship of the AE to IP administration makes a

causal relationship possible, and other medications, therapeutic interventions, or underlying conditions do not provide a sufficient

explanation for the observed event.

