1.0 Objectives

1.1 Primary Objective

The primary objectives of the study are:

- 1.1.1 The primary objective of the study is to determine the complete response (CR) rate of SGI-110 with or without donor lymphocyte infusion (DLI) either for the treatment of morphologic relapse or the presence of MRD in patients with acute myeloid leukemia or myelodysplastic syndrome after hematopoietic stem cell transplantation in patients with AML and MDS (cohort 1 and 2).
- 1.1.2 The primary objective of the study is the relapse-free survival with the use of SGI-110 as maintenance therapy in patients with high risk acute myeloid leukemia or myelodysplastic syndrome after hematopoietic stem cell transplantation (cohort 3).
- 1.2. Secondary Objectives

The secondary objectives of the study are:

- 1.2.1 To determine the safety and toxicity of SGI-110 with or without DLI in this subject population.
- 1.2.2 To evaluate overall response and survival.
- 1.3 Study Endpoints
 - 1.3.1 Primary Endpoint

The primary endpoint is the CR rate of SGI-110 after enrollment to the clinical trial for cohorts 1 and 2. The primary endpoint is relapse free survival for cohort 3.

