2.8 Efficacy of DLI

The efficacy of donor lymphocyte infusion (DLI) varies with the underlying malignancy, the dose of infused lymphocytes, and the degree of host lymphodepletion. Outcomes are best for patients with chronic phase chronic myeloid leukemia (CML) followed by patients with lymphoma, multiple myeloma, and acute leukemia (mostly acute myeloid leukemia). Initial studies also suggest that the presence of host-derived regulatory T cells decreases the antitumor effect (28). Patients who respond to DLI will usually demonstrate a clinical response within two to three months, but a full response may take one year or longer(14). Responses can be durable with reports of responses lasting up to 20 years.

Data regarding the efficacy of donor lymphocyte infusions (DLI) come primarily from small case series and two large retrospective studies from Europe and North America:

- The European Group for Blood and Marrow Transplantation reported the results with DLI obtained from 84 patients with chronic myeloid leukemia (CML), 23 with acute myeloid leukemia (AML) and 22 with acute lymphoblastic leukemia (ALL) (29). In this retrospective analysis, 73 percent of patients with relapsed CML had a complete remission after DLI. Remissions, whether defined by molecular or hematologic criteria, were durable. Patients with AML and ALL did not respond as well, as only 29 and zero percent developed a complete remission, respectively. DLI treatment was associated with substantial toxicity: 41 percent developed clinically significant GVHD; 41 percent suffered from myelosuppression; and 13 percent died of causes other than their underlying malignancy.
- A second retrospective analysis (from 25 North American programs) reported the outcomes after DLI in 140 allogeneic transplant patients who relapsed (30). A response rate of 60 percent was observed for patients with CML. The responses were superior in patients with

only cytogenetic relapse or for those treated with DLI while in chronic phase, compared with those who had progressed to either accelerated or blast phases. As in the European study, the results were not as favorable among patients with AML or ALL (15 and 18 percent complete response, respectively). Complications included GVHD (60 percent) and pancytopenia (19 percent).

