8.3 Reporting of Serious Adverse Events

Any AE that meets any criterion for an SAE requires the completion of an SAE Report Form in addition to being recorded on the AE page/screen of the eCRF. All SAEs must be reported to Astex Drug Safety within 24 hours of the investigator's knowledge of the event by facsimile, or other appropriate method, using the SAE Report Form, or approved equivalent form. This instruction pertains to initial SAE reports as well as any follow-up reports.

The investigator is required to ensure that the data on these forms is accurate and consistent. This requirement applies to all SAEs (regardless of relationship to IP) that occur during the study (from the time the subject signs informed consent to 30 days after the last dose of IP), and those made known to the investigator at anytime thereafter that are suspected of being related to IP. Serious AEs occurring prior to treatment but after informed consent will be collected.

The SAE report should provide a detailed description of the SAE and include a summary of hospital records and other relevant documents. If a subject died and an autopsy has been performed, copies of the autopsy report and death certificate are to be sent to Astex Drug Safety as soon as these become available. Any follow-up data will be detailed in a subsequent SAE Report Form, or approved equivalent form, and sent to Astex Drug Safety.

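### Relatedness is judged against IP alone, so non-serious, non-GVHD toxicity explained by the protocol's own DLI can go unrecorded in cohorts 1 and 2, although safety with DLI is a stated objective

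*Combined protocol and SAP*

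**What the plan says.** Section 4.6.1 plans three DLI infusions in cohorts 1 and 2 for patients who meet the criteria. The first is on day 6 of SGI-110 cycle 2 (4.6.3), and further infusions are permitted on day 6 of cycles 4 and 6 (4.6.4). Objective 1.2.1 reads: "To determine the safety and toxicity of SGI-110 with or without DLI in this subject population". The matching endpoint, 1.3.2.1, is narrower: "Safety (type, frequency, severity of AEs and relationship of AEs to SGI-110".

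Section 8.2.3 sets a two-way causality call: "The investigator must determine the relationship between the administration of IP and the occurrence of an AE/SAE as Not Suspected or Suspected". Not Suspected applies, among other cases, when other "medications, therapeutic interventions, or underlying conditions provide" a sufficient explanation. DLI is not excepted. Section 8.1 introduces the abbreviation IP only generically ("sensitivity or toxicity to an investigational product (IP) should be reported as an AE") and then limits recording: "Only related adverse events and SAEs will be recorded on the AE page of the eCRF". Its window for related AEs closes 30 days after the last IP dose.

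Section 8.3 requires all SAEs within that window whatever their attribution. Later SAEs are required only in the case of "and those made known to the investigator at anytime thereafter that are suspected of being related to IP". Section 8.5 has its own late-SAE rule for the IND Office, tied to study treatment rather than to IP. The recommended AE recording table at the end of 8.2.1 grades recording by phase, severity and five attribution categories.

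**The concern.** Two treatments are given one day apart under the same protocol, and only one of them counts when an event is classed as related. The other falls among the alternative explanations that make an event unrelated. Since relatedness decides whether a non-serious event is recorded at all, the recording rule depends on whether the patient received DLI.

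The protocol itself treats DLI as toxic. Section 2.8 cites a retrospective series in which 41% had myelosuppression and another of which it says: "Complications included GVHD (60 percent) and pancytopenia (19 percent"). A safety summary meant to describe SGI-110 with or without DLI would be thinnest where DLI adds its own non-GVHD toxicity. The primary endpoints, CR rate and relapse-free survival, are not defined by attribution and are not affected.

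**Working it through.** No sample size or operating characteristic enters this point. The check sets the rules side by side and follows one event through them.

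**Step 1: what IP means.** No section defines it. Endpoint 1.3.2.1 names only SGI-110, and 8.2.5 speaks of discontinuing or reducing IP, which fits a drug dosed in cycles. SGI-110 is the natural reading, but it is an inference.

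**Step 2: one event, two patients.** Take the same non-serious, non-GVHD event in two cohort 1 patients, with timing that fits SGI-110.

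| | Patient without DLI | Patient given DLI |
|---|---|---|
| Other sufficient explanation (8.2.3) | None | DLI, if judged sufficient |
| Causality call | Suspected | Not Suspected |
| 8.1, if non-serious | Recorded | Not recorded |

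Suspected requires that other interventions do not sufficiently explain the event. One that DLI could explain is therefore Not Suspected even if SGI-110 contributed.

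**Step 3: the two recording rules for a non-serious, non-GVHD event explained by DLI.**

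| Grade | 8.1 text | Table in 8.2.1, Phase II, Unrelated or Unlikely |
|---|---|---|
| 1-2 | Not recorded | Not recorded |
| 3-4 | Not recorded | Appears to be recorded |

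The table is damaged in the text available; the Grade 3 cell for Unlikely is garbled but seems to include Phase II. The table is headed as recommended and uses five attribution categories against the two in 8.2.3, with no mapping between them. So the Grade 1-2 loss follows from both rules, while Grade 3-4 capture is contradictory. Even where an event is captured, nothing attributes it to DLI.

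**Step 4: what is captured regardless.** All SAEs in the window (8.3), and GVHD as its own endpoint without an attribution filter (1.3.2.4).

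**Step 5: late SAEs.** Section 8.3, which governs reports to the drug company, takes only those suspected of being related to IP. Section 8.5 sends those related to study treatment to the IND Office, wording that can include DLI. The gap is in 8.3 only.

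**Step 6: the window.** The last SGI-110 dose of a cycle is on day 5, so the window closes on day 5 + 30 = 35. DLI on day 6 leaves 35 - 6 = 29 days. If day 6 is a Saturday and DLI moves to Monday (day 8), 35 - 8 = 27 days remain. Anchoring on a DLI given on schedule would add 36 - 35 = 1 day, so the window is not the substance of this point.

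**The case against.** The strongest reply is that IP is merely undefined. If the sponsor meant it to include DLI, the loss disappears. That is fair, and the conclusion is conditional on reading IP as SGI-110. But 1.3.2.1 and 8.2.5 favour that reading, and under the other one the text still needs a definition and 1.3.2.1 still does not match 1.2.1.

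A second reply is that investigators may readily call an event Suspected. Myelosuppression is a listed SGI-110 risk (2.5), and DLI follows the fifth dose by a day. For cytopenias this has force. In active disease or persistent MRD, 4.4.1 moreover presumes that low counts come from disease. It limits how often the rule bites but does not remove the rule.

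A third reply is that an attribution field cannot cleanly separate treatments given a day apart, without a randomised DLI comparison. That stands. The main gain is that events are recorded at all; attribution will often be to both.

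A reader might go further in three ways that the documents do not support:

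- **That objective 1.2.1 cannot be answered.** SAEs within the window and GVHD are collected whatever their attribution, and GVHD status is followed after discontinuation (8.4), although 5.3.6 ends follow-up for non-responders at cycle 6. The summary is distorted, not empty.
- **That late DLI-related SAEs escape reporting.** Section 8.5 covers them.
- **That a number of affected patients follows from multiplying the cytopenia rates in 2.8 by expected DLI recipients.** That would take every cytopenia as non-serious and as attributed to DLI rather than to SGI-110 or disease, and would transfer rates from mixed series (the 41% series had 84 CML patients among 129, and 23 with AML). Section 8.2.7 also counts a laboratory abnormality as an AE only in certain circumstances.

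**Conclusion.** The point holds in a limited form. Followed as written, and with IP read as SGI-110, Sections 8.1 and 8.2.3 remove non-serious, non-GVHD events that DLI sufficiently explains. Grade 1-2 events are lost under both recording rules; for Grade 3-4 the rules conflict. Recording then depends on whether DLI was given, which distorts the with-or-without-DLI safety summary and can lower the SGI-110 related-event count among DLI recipients. Analysis cannot be relied on to restore these events, because 8.1 applies the same limit to source documents; scheduled blood counts (5.1, 5.2) would help only for laboratory findings.

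The size cannot be given in patients: the documents do not say how DLI toxicity divides by seriousness, grade or attribution. The late-SAE part is a mismatch between 8.3 and 8.5. The fault lies in secondary safety reporting and is worth correcting because the correction is cheap.

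**What to change.** For cohorts 1 and 2:

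- Define study treatment for attribution in 1.3.2.1, 8.1, 8.2.3 and 8.3 as SGI-110 and DLI, and define IP.
- State in 8.2.3 that DLI does not count as an other therapeutic intervention.
- Record events suspected of being related to either treatment, with attribution to SGI-110, DLI, both or neither.
- Reconcile 8.1 with the recording table in 8.2.1, including the two-category and five-category scales, so that Grade 3-4 recording is unambiguous.
- Reconcile the late-SAE rule in 8.3 with that in 8.5.

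The cost is one more eCRF field, wording changes in 1.3.2.1 and Section 8, and a few more events to record. Treatment, eligibility and sample size do not change.
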